#### **DVT and PE specific definitions;**

To meet the criteria for new or progressive DVT one of the following criteria must be met:

1. A new intraluminal filling defect in two or more projections on venography (New VTE).
2. 5 cm or more extension or an intraluminal filling defect previously seen on ultrasound or venography (progression of VTE).
3. Presence of intraluminal thrombus.

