## 9. ASSESSMENTS AND ENDPOINT DEFINITIONS

### 9.1. Endpoint Definitions

#### 9.1.1. VTE Endpoints

A suspected new or progressive symptomatic VTE, in the same anatomical region, should be documented with the same imaging method used at Screening/Baseline. Suspected new or progressive VTE in a different anatomical region should be documented utilizing institutional standards. These images should be collected and be included in the primary source records. Thrombus resolution of the qualifying event will be measured by repeat imaging at the EOS visit (using the same modality as that which was used to diagnosis the thrombosis prior to enrollment). If an image has been captured prior to the EOS and it demonstrates complete resolution of the qualifying VTE, then a repeat image does not need to be done again at day 90. For purposes of the study, the complete resolution image will be the “EOS” image for the index event.

In the assessment of a new or progressive symptomatic thrombus, the following general definitions will be utilized;

**Symptomatic New VTE:** Symptomatic VTE confirmed by at least one radiographic test. Asymptomatic VTE within a venous segment noted to be patent on a prior imaging study. Symptomatic will be defined as: New or progressive signs and symptoms as judged by the investigator including but not limited to:

- Objective swelling;
- Pain or tenderness;
- Pitting edema;
- Erythema or cyanosis.

**All New VTE:** All VTE confirmed by at least one radiographic test.

**Stable VTE:** Follow-up study demonstrating stable clot burden utilizing the same imaging modality as the Screening Visit.

**Regression of VTE:** Follow-up study demonstrating regressed clot burden utilizing the same imaging modality as the Screening Visit.

**Progression of VTE:** Progression of clot burden on a follow-up study in terms of severity of occlusion, or involvement of new venous segments at any time after the initial diagnosis.

In the assessment of a new or recurrent PE, the following general definitions will be utilized;

**New PE:** Symptomatic PE confirmed by presence of an intraluminal filling defect of the pulmonary artery on CT angiography and/or a mismatched defect on a nuclear V/Q scan. All new PE's will be considered to be a symptomatic event.

**Stable PE:** Follow-up study demonstrating stable clot burden utilizing the same imaging modality as the Screening Visit.

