#### **PE Specific Definition:**

To meet the criteria for new or progressive PE one of the following criteria must be met:

1. A new intraluminal filling defect or a sudden cut-off of vessels more than 2.5 mm in diameter on a pulmonary angiogram.

2. An intraluminal filling defect on CT angiography involving the main pulmonary artery, or proximal generations of the branch pulmonary arteries that are reliably evaluated by CT.
3. High probability V/Q scans.

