##### **6.1.2.1. Efficacy Analysis**

- Proportion of subjects with objectively documented new or progressive symptomatic VTE during dalteparin treatment.

The count and proportion will be summarized overall and by each age group, along with the two-sided exact 95% CI.

- Relationship between objective documented new or progressive symptomatic VTE assessed by investigators and the anti-Xa level during dalteparin treatment.

Logistic regression for new/progressive VTE assessed by investigators on anti-Xa level at end of dose adjustment and other prognostic factors (eg, age, baseline tumor status), will be performed. For each of the covariates, the odds ratio, and the corresponding 95% CI, will be displayed.

Subjects who experience at least one new or progressive VTE while on study will be counted as Yes.

- Time to event (first episode of recurrent VTE) during dalteparin treatment.

The time to event (first recurrent VTE) will be described by using the Kaplan-Meier method. In addition, the Cox Proportional Hazard Regression model will be employed to assess the hazard ratio of the event with prognostic factors.

See [Appendix 1](#) for a general description of censoring of time-to-event variables.

- Proportions of subjects with progression, regression, resolution and no change in the qualifying VTE (in comparison with the assessment at study entry) during dalteparin treatment.

The count and proportion will be summarized overall and by each age group, along with the two-sided exact 95% CI.

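### Protocol Section 9.1.1 gives three conflicting rules for DVT progression, one of them a 5 cm length not scaled to body size, and does not say which one governs

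*Protocol*

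**What the plan says.** Protocol Section 9.1.1 first gives general definitions. Progression of VTE is "Progression of clot burden on a follow-up study in terms of severity of occlusion, or involvement of new venous segments at any time" after the first diagnosis. Stable and regressed VTE are also defined by clot burden on the follow-up image, without a length. For PE, progression means that new pulmonary arterial segments are involved, but only within 14 days of the first diagnosis. A linking sentence then says that set criteria, depending on where the clot lies and how it was imaged, will be used to apply the definitions.

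Two specific lists follow. The DVT list opens: "To meet the criteria for new or progressive DVT one of the following criteria must be met".

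- Item 1 is a new filling defect in at least two venographic projections, labelled as new VTE.
- Item 2, the only one labelled progression, is "5 cm or more extension or an intraluminal filling defect previously seen on ultrasound or venography (progression of VTE").
- Item 3, unlabelled, is "Presence of intraluminal thrombus".

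The PE list also has three alternatives. The first is "A new intraluminal filling defect or a sudden cut-off of vessels more than 2.5 mm in diameter on a pulmonary angiogram"; those for CT angiography and V/Q scanning carry no calibre limit.

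Section 6.2 accepts CT and MRI without venography as entry images. Section 6.3 admits children above 3.0 kg and up to 100 kg. Protocol Section 12.3.5 and SAP Section 6.1.2.1 summarise "Proportions of subjects with progression, regression, resolution and no change in the qualifying VTE" overall and by age group, with exact 95% confidence intervals. The SAP adds no definition of progression.

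**The concern.** Every child enters the study with a thrombus, so the definition has to separate a growing clot from an old one that is unchanged or shrinking. Section 9.1.1 offers three tests that need not agree and does not say which takes precedence. Criterion 2 is also an absolute length, applied from newborns to teenagers, and names only ultrasound and venography. Nothing in the section scales it to age, height or weight.

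The four-way outcome of the qualifying clot and the proportion with new or progressive symptomatic VTE both depend on this choice. SAP Section 3.3.2 makes examination of safety and efficacy within age groups an objective, and Protocol Section 12.3.5 names age group as an example factor in the Cox model for recurrent VTE. The document history records that the central imaging reader and the adjudication committee were removed, so investigators at about 40 sites must choose a rule for themselves.

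**Working it through.** The plan states no figure to reproduce on this point. The check is a side-by-side reading of the rules, followed by an illustration of scale.

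**Step 1. The three rules applied to the same follow-up image.** The four cases are hypothetical.

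| Follow-up finding | General definition | Criterion 2 (5 cm) | Criterion 3 (thrombus present) |
|---|---|---|---|
| Clot grows 2 cm and enters a new venous segment | Progression | Not met | Met |
| Same length, occlusion becomes more severe | Progression | Not met | Met |
| Clot grows 5 cm or more inside the same segment, occlusion unchanged | Neither listed feature present | Met | Met |
| Clot shrinks but is still visible | Regression | Not met | Met |

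No row gives the same answer under all three rules. Criterion 3 is met in every row because the qualifying clot itself satisfies it, so it cannot distinguish progression from no change or regression. The table reads criterion 2 as an extension of a filling defect already seen. As printed, with *or* in place of *of*, its second half would also be met by any old defect.

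**Step 2. What a fixed 5 cm means across body sizes.** Inputs: 5 cm (Section 9.1.1) and the example weights of 4, 7, 12, 24 and 82 kg (Protocol Appendix 2). Assumption, not from the documents: linear body dimension is proportional to weight^(1/3), with exponents 0.25 and 0.40 as the range.

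- Ratio of the 82 kg teenager to the 4 kg newborn: (82/4)^(1/3) = 20.5^(1/3) = 2.74.
- 5 cm at 4 kg corresponds to 5 × 2.74 = 13.7 cm at 82 kg.
- In the other direction, 5 cm at 82 kg corresponds to 5 / 2.74 = 1.8 cm at 4 kg.
- Exponent 0.25: ratio 2.13, giving 10.6 cm. Exponent 0.40: ratio 3.35, giving 16.7 cm.
- For the other example weights, with exponent 1/3, 5 cm corresponds at 82 kg to 11.4 cm (7 kg), 9.5 cm (12 kg) and 7.5 cm (24 kg).

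This gives a direction for criterion 2 used alone. It does not count missed events, because the documents give no vein lengths, clot extensions or event rates by age.

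**Step 3. How much one reclassified child matters.** Assume 10 children in an age group, the largest stratum size listed in Protocol Section 12.1; enrolment sets no quota per group. One child moves the proportion by 1/10 = 10 percentage points. The exact Clopper-Pearson 95% interval is 0 to 30.8% for 0/10 and 0.3 to 44.5% for 1/10.

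**Step 4. PE.** The 2.5 mm limit belongs to one of three alternatives, so a PE can be registered without it. The time limit matters more. Section 5.3 places end of study at Day 90 ± 14, so no earlier than 90 − 14 = Day 76. If the 14 days refer to when the change is seen, an extension first found on the end-of-study image cannot count as PE progression, whereas the VTE definition sets no time limit.

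**The case against.** The strongest reply is that the size-free rule is already in the protocol. The general definitions of stable, regressed and progressive VTE correspond closely to the reported categories, apply at any body size and are not restricted by modality. The DVT list asks for only one of three items, and item 3 has no size limit. The endpoints are secondary and their objectives are worded as exploratory. SAP Section 5.1 tests no hypotheses, and with about 10 children per group the intervals are wide under any definition.

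Most of this stands, and it defeats a stronger reading. A reader might infer that DVT progression cannot be recorded without 5 cm of extension, so that newborns and infants look better by construction. The documents do not support that. It would be true only if criterion 2 were used alone, and nothing says that a shorter extension is to be recorded as no change. If criterion 3 were taken literally, the error would run the other way, towards too many progressions at every age. Nor is a bias shown for PE from the 2.5 mm limit.

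The reply does not show that the general definition takes precedence. The linking sentence points towards location- and modality-specific criteria, and the DVT and PE lists are the only ones given. Criterion 3 does not rescue the plan either, since it does not separate the categories to be reported.

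**Conclusion.** The point holds as a conflict of definitions. Section 9.1.1 contains three rules for DVT progression that disagree on ordinary follow-up findings, and neither document says which governs. That follows from the text alone.

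The effect of body size is conditional. If criterion 2 is applied by itself, progression is harder to register in smaller children: 5 cm in a 4 kg child corresponds to roughly 10.6 to 16.7 cm in an 82 kg teenager, under an assumed scaling of length with weight. How many children would be reclassified, and whether the by-age tables would shift in one direction overall, cannot be determined from the documents. The 2.5 mm limit is a minor matter. Because the endpoints are secondary and descriptive, the primary PD results are untouched. The correction is still worth making, since the tables cannot be interpreted unless every site uses the same rule.

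**What to change.** In Protocol Section 9.1.1, with a matching statement in SAP Section 6.1.2.1:

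1. State that the general definitions, for VTE and for PE, govern the progression, regression and no-change classification at every age and for every accepted imaging modality.
2. Restrict DVT criterion 3 to thrombus not present on the qualifying image.
3. Reconcile the 14-day limit in the PE progression definition with the open-ended VTE definition, and say how a change first seen at end of study is classified.
4. Keep the 5 cm extension and, secondarily, the 2.5 mm angiogram limit as recorded descriptors, and add a sensitivity table by age group that uses them.

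This concerns classification for analysis only. Protocol Sections 7 and 8.2 also list new or progressive VTE among the reasons for ending treatment; nothing is proposed there.

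The cost is wording in two documents and one extra table. No new imaging is needed, because copies of all images are kept with the source documents and children already assessed can be reclassified from them. The downside is that judgements of occlusion and segment are somewhat more subjective than a measured length, which the sensitivity table partly offsets.

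### As written, Protocol 9.1.1 lets a residual qualifying clot, re-imaged for new symptoms, count as new or progressive symptomatic VTE, and it also places asymptomatic VTE under the symptomatic definition

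*Protocol*

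**What the plan says.** Imaging-confirmed VTE is an entry requirement (Protocol 6.2, criterion 1), so every child has a qualifying clot at baseline.

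Protocol 9.1.1 first gives general definitions. *Symptomatic New VTE* is symptomatic VTE with at least one confirming image, and the next sentence of the same definition adds "Asymptomatic VTE within a venous segment noted to be patent on a prior imaging study". Symptomatic means new or worsening signs in the investigator's judgement. *New PE* is a symptomatic PE shown by a filling defect on CT angiography or a mismatched V/Q defect. *Stable VTE* is a "Follow-up study demonstrating stable clot burden utilizing the same imaging modality as the Screening Visit"; *Regression* is worded in parallel. *Progression of VTE* is judged "in terms of severity of occlusion, or involvement of new venous segments at any time after the initial diagnosis".

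Specific lists follow. The DVT list opens with "To meet the criteria for new or progressive DVT one of the following criteria must be met". Criterion 1 asks for a new defect on venography. Criterion 2 reads "5 cm or more extension or an intraluminal filling defect previously seen on ultrasound or venography". Criterion 3 is, in full, "Presence of intraluminal thrombus". The PE list works in the same any-one-of-three way. Its criterion 2 begins "An intraluminal filling defect on CT angiography involving the main pulmonary artery" and its criterion 3 is "High probability V/Q scans".

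The SAP (3.2 and 6.1.2.1) uses new or progressive symptomatic VTE as a secondary efficacy endpoint and adds no definition. SAP Section 1 records that central image reading and the adjudication committee were dropped. Protocol Sections 7 and 8.2 end dalteparin on new or progressive VTE, with or without symptoms.

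**The concern.** Persisting thrombus is not treatment failure, but a criterion that asks only whether thrombus is present cannot tell the two apart. A child whose clot is unchanged or shrinking, and who is scanned because of new pain or swelling, could be recorded as a failure.

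Three planned analyses draw on these events: the proportion with new or progressive symptomatic VTE, the time to first recurrent VTE, and the regression of VTE on anti-Xa level. The time-to-event effect is an inference, because the lists do not themselves define *recurrent*. The same text also decides whether a child stays on dalteparin. Investigators apply it directly, and no later step in the documents would reconcile two sites that read it differently.

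The asymptomatic sentence is a separate problem: it puts silent events into an endpoint labelled symptomatic.

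**Working it through.** The plan gives no expected VTE rate, margin or power for this endpoint, so there is no figure to reproduce. The check is mainly textual.

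**Step 1. Does each rule in Protocol 9.1.1 require a change from the qualifying event?**

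| Rule | Change required? |
|---|---|
| DVT criterion 1 | Yes, the defect must be new |
| DVT criterion 2, as printed | Not on a literal reading: extension *or* a defect seen before. Yes if *or* is a slip for *of*, which is likely |
| DVT criterion 3 | No |
| PE criterion 1 | Yes for its first limb (new defect) |
| PE criteria 2 and 3 | No |
| *Symptomatic New VTE*, first sentence | No; newness attaches to the symptoms |
| *Symptomatic New VTE*, asymptomatic sentence | Yes, the segment must earlier have been patent; but no symptoms are needed |
| *New PE* | No |
| *Stable*, *Regression* | Defined by clot burden at follow-up |

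**Step 2. Apply the rules to one child.** Take an unchanged qualifying leg DVT, new swelling, and a repeat scan by the entry method. Symptoms plus one positive image satisfy *Symptomatic New VTE*. Criterion 3 is met, and one criterion is enough. The child is an event. The same scan also meets *Stable VTE*. A residual PE with new symptoms behaves the same way through PE criterion 2 or 3.

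**Step 3. Look for a tie-break.** Section 9.1.1 says the general definitions are to be determined by set criteria that depend on clot location and modality. The only such criteria in the documents are the two lists. No sentence ranks *Stable* or *Regression* above them.

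**Step 4. Compare the two progression tests.** A 3 cm extension into a new segment meets the general definition but not the 5 cm test. A 6 cm extension within one segment, with occlusion unchanged, does the reverse. While criterion 3 stands, both children already qualify as new or progressive DVT, so for now the conflict changes only the progression label.

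**Step 5. Scale, for illustration.** Inputs: N = 50 (target in Protocol 6.1), the SAP 5.2.1 Clopper-Pearson interval, and an assumed x miscounted children with no true events. Each miscounted child adds 100/50 = 2 points. The limits are the 2.5% quantile of Beta(x, N − x + 1) and the 97.5% quantile of Beta(x + 1, N − x). For x = 0 the lower limit is 0 and the upper limit is 1 − 0.025^(1/N) = 1 − 0.025^(1/50) = 7.1%.

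| x of 50 | Proportion | Exact 95% CI |
|---|---|---|
| 0 | 0% | 0 to 7.1 |
| 1 | 2% | 0.1 to 10.6 |
| 3 | 6% | 1.3 to 16.5 |
| 5 | 10% | 3.3 to 21.8 |

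In an age group of 10, one child moves 0% (0 to 30.8) to 10% (0.3 to 44.5). The size of 10 is an assumption. Section 12.1 mentions up to 10 per stratum, Appendix 3 mentions 10 to 40, and no quota is set.

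**The case against.** The strongest reply is that context already excludes unchanged clot. The lists are headed as criteria for new or progressive disease. *Stable* and *Regression* are among the definitions to be used in that assessment. A suspected event in the same region must be imaged by the baseline method, and Section 4 repeats this for the endpoint; the main use of that rule is comparison with baseline. A sensible investigator could therefore call the scan stable. This stands as evidence of intent, but it supplies no overriding rule, and criterion 3 remains sufficient as printed.

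It is also fair to say that the harm needs several things together: new symptoms, imaging prompted by them, only residual clot on the image, and an investigator who follows the list rather than the *Stable* definition. The VTE objectives are exploratory and the SAP tests no hypotheses (5.1). That limits the weight of the point without removing it.

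Four stronger readings are tempting and are not supported:

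- **Silent residual clot at the scheduled Visit 7 scan inflates the endpoint.** The endpoint requires symptoms, so such a scan does not become an event by this route.
- **The asymptomatic sentence lets residual clot in.** It requires a segment earlier shown to be patent.
- **The two progression tests change the event count today.** Step 4 shows that they do not.
- **The dose findings are affected.** The primary PD endpoints do not use these definitions.

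**Conclusion.** The point holds as a defect in a stated rule. Read as written, Protocol 9.1.1 can score residual qualifying clot, re-imaged for new symptoms, as new or progressive symptomatic VTE. The same scan can be called stable, and nothing settles which label wins. The drafters evidently meant otherwise, so this is careless wording and not a deliberate choice. The asymptomatic sentence contradicts the endpoint's own label.

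The reach is limited to exploratory secondary VTE analyses and the rule ending dalteparin. After entry, imaging is scheduled only at Visit 7 or early termination, so the stopping rule is exposed mainly through event-driven or discretionary scans.

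The size cannot be estimated from the documents. What follows from arithmetic alone is 2 percentage points per miscounted child at N = 50. The counts of 1 to 5, the absence of true events and the age group of 10 are assumptions. That two sites would in fact score the same image differently is a possibility the text allows; the documents do not show it happening.

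**What to change.** 1. State that residual qualifying thrombus meeting *Stable* or *Regression* is not a new or progressive event, for both the endpoints and the stopping rule. Judge this against the latest earlier image of that region, so that regrowth after partial regression still counts.
2. Limit DVT criterion 3, PE criteria 2 and 3 and *New PE* to thrombus or a defect that either is not part of the qualifying VTE (in a segment patent on, or not covered by, prior imaging) or meets the progression definition. Including regions not imaged before keeps a first PE, or a DVT at a new site, countable. In DVT criterion 2, change *or* to *of* after *extension*.
3. Move the asymptomatic sentence to *All New VTE*, and exclude residual qualifying clot there.
4. Once criterion 3 is corrected, state which progression test governs: occlusion severity or new segments, or extension of 5 cm or more.

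The cost is protocol wording, carried into the SAP where needed, with no new patients, visits or imaging. There are three downsides. VTE events already recorded may need re-checking against the images that sites are told to keep (Protocol 9.1.6). One scan may be an event against the latest image yet a regression from entry in the progression/regression table, because SAP 6.1.2.1 compares that table with study entry; a footnote should say so. In a region never imaged before, an old silent clot could still be counted as new, which is accepted so that true events there are not missed.

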#### **PE Specific Definition:**

To meet the criteria for new or progressive PE one of the following criteria must be met:

1. A new intraluminal filling defect or a sudden cut-off of vessels more than 2.5 mm in diameter on a pulmonary angiogram.

2. An intraluminal filling defect on CT angiography involving the main pulmonary artery, or proximal generations of the branch pulmonary arteries that are reliably evaluated by CT.
3. High probability V/Q scans.

